## 12.2.2 Serious Adverse Events (SAEs)

## 12.2.2.1 Site Requirements for Reporting SAEs to BTCRC Administrative Headquarters

- SAEs will be reported from time of signed informed consent until 100 days after discontinuation of study drug(s) or until a new anti-cancer treatment starts, whichever is earlier.
- SAEs will be reported on the SAE Submission Form and entered in the SAE tab in OnCore within 1 business day of discovery of the event.
- SAEs include events related and unrelated to the study drug(s).
- All SAEs will be recorded in the subject's medical record and on the appropriate study specific eCRF form(s) within OnCore.
- All SAEs regardless of relation to study drug will be followed until resolution to ≤ Grade 1 or baseline and/or deemed clinically insignificant and/or until a new anti-cancer treatment starts, whichever occurs first.

The site will submit the completed SAE Submission Form (see Documents/Info tab of the EDC) to BTCRC AHQ within **1 business day** of discovery of the event. The form may be sent electronically to [contact]. The site investigator is responsible for informing the IRB and/or other local regulatory bodies of the SAE as per local requirements.

The original copy of the SAE Submission Form and the email correspondence must be kept within the study file at the study site.

Once the SAE has resolved, sites must submit a follow up SAE Submission Form within a reasonable timeframe to BTCRC AHQ electronically at [contact].

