## 13.8 Interim Analysis/Criteria for Stopping Study

After the 10th subject in each arm is treated with at least one dose of study drug and observed for a minimum of 3 months after first dose of study therapy, "unacceptable toxicities warranting early closure of the trial" will be evaluated, defined as a) any definitely related immunotherapy death; or b) any unexpected and previously unreported grade 4 toxicities definitely related to immunotherapy. If such events are observed in one subject, the DSMB will discuss and provide recommendations to the sponsor-investigator whether to terminate the appropriate arm. If such events are observed in two or more of the first 10 subjects, the arm will be terminated. Each arm will be analyzed separately and may result in different actions per arm.

After the 25th subject in each arm is treated with at least one dose of study drug and observed for a minimum of 3 months after first dose of study therapy, "unacceptable toxicities warranting early closure of the trial" will again be evaluated and defined as a) any definitely related immunotherapy death ; or b) any unexpected and previously unreported grade 4 toxicities definitely related to immunotherapy. If such events are observed in two subjects, the DSMB will discuss and provide recommendations to the sponsor-investigator whether to terminate the arm. If such events are observed in three or more of the first 25 subjects, the arm will be terminated. Each arm will be analyzed separately and may result in different actions per arm.

Pneumonitis of grade 3 and 4 will be continuously monitored. An overall rate of 20% or above would be considered unacceptable. If the probability of the grade 3/4 pneumonitis rate being less than 20% drops below 0.1, the arm will be terminated. A priori, the rate is assumed to follow  $\theta \sim beta(1,1)$ . Conditional on observing *y* events out of *n* subjects, the rate follows  $\theta|y,n\sim beta(1+y,1+n-y)$ . The probability of  $\theta < 20\%$  is  $\int_0^{0.2} f(\theta|n, y)d\theta$ . The threshold (k) is defined as the smallest *y* corresponding to the integral being smaller than 0.1, which will lead to termination of the arm.

Ν	10	11	12	13	14	15	16	17	18	19	20	21	22	23	24
k	4	4	4	5	5	5	6	6	6	6	7	7	7	7	8
Ν	25	26	27	28	29	30	31	32	33	34	35	36	37	38	39
k	8	8	8	9	9	9	9	10	10	10	10	11	11	11	11
Ν	40	41	42	43	44	45	46	47	48	49	50	51	52	53	54
k	12	12	12	12	12	13	13	13	13	14	14	14	14	15	15

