## 14.2 Data Safety Monitoring Board

This study will have a Data and Safety Monitoring Board (DSMB). The DSMB is chaired by an independent medical oncologist external to this trial. The DSMB will provide a recommendation to the sponsor-investigator after all information is reviewed. This information will also be provided to BTCRC AHQ who will distribute to the site investigator/participating sites for submission to their respective IRB according to the local IRB's policies and procedures.

The DSMB will meet after the first 10 subjects are treated with at least one dose of study drug and observed for a minimum of 3 months after first dose of study therapy, in each arm respectively. Accrual will not be held while the DSMB review is pending. Each arm will be scrutinized separately and may result in different actions per arm.

The DSMB will also meet after the first 25 subjects are treated with at least one dose of study drug and observed for a minimum of 3 months after first dose of study therapy, in each arm respectively. Accrual will not be held while the DSMB review is pending. Each arm will be scrutinized separately and may result in different actions per arm.

From the time of first subject enrollment until the last subect completes study drug administration, the DSMB will conduct reviews at least twice a year.

The DSMB review will include but is not limited to:

- Study accrual patterns
- Treatment regimen information
- Adverse event summary report
- Summary of any deaths on study including cause of death
- Audit and/or monitoring results, if applicable
- Protocol deviations

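### The continuous pneumonitis stopping rule counts grade 3 and 4 only, so a case recorded only as grade 5 is scored as a non-event and makes the arm look safer

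*Combined protocol and SAP*

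**What the plan says.** Section 13.8 names the monitored event twice, first in "Pneumonitis of grade 3 and 4 will be continuously monitored" and then in the criterion: "If the probability of the grade 3/4 pneumonitis rate being less than 20% drops below 0.1, the arm will be terminated". The limit is "An overall rate of 20% or above would be considered unacceptable". The prior is Beta(1,1). After y events in n subjects the posterior is Beta(1+y, 1+n−y), and a table gives the stopping count k for N=10 to 54. The section does not mention grade 5, or say whether a counted case stays counted if the subject later dies. Section 13.7.3, by contrast, uses grades 2 to 5 for the exploratory pneumonitis analysis, so the plan does recognise fatal pneumonitis as an outcome.

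Other provisions that touch on deaths:

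- **Death rule, section 13.8.** It counts "any definitely related immunotherapy death" (together with certain unexpected grade 4 toxicities). It is evaluated after the 10th and 25th subject in each arm. One subject with such an event at the first look, or two at the second, leads to DSMB discussion. Two of 10 or three of 25 terminates the arm.
- **DSMB, section 14.2.** The material reviewed includes "Summary of any deaths on study including cause of death", and until the last subject completes study drug "the DSMB will conduct reviews at least twice a year".
- **SAE reporting, section 12.2.2.1.** SAEs are to be "entered in the SAE tab in OnCore within 1 business day of discovery of the event".

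**The concern.** The model has two classes only: y events and n−y non-events. A treated subject whose pneumonitis is recorded only as grade 5 is in n. Because the event is defined as grade 3 or 4, that subject is not in y. The worst form of the toxicity being monitored therefore raises the posterior probability that the arm is safe.

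This matters because the rule is binding: once the boundary is crossed, the arm is terminated. If it is unclear whether fatal cases count, two people applying the rule to the same data can reach opposite termination decisions.

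The concern is limited to cases never recorded as grade 3 or 4. A case first recorded at one of those grades and later fatal is presumably already counted, although the text does not say so.

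**Working it through.** **Inputs, all from section 13.8:** prior Beta(1,1); limit 20%; stop when P(θ<0.20) is below 0.1; printed k for N=10 to 54. Planned maximum enrolment is 54 in Arm 1 and 51 in Arm 2 (section 13.3).

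**Step 1: reproduce the plan's table.** For each n, k is the smallest y for which P(θ<0.2 | y, n) = Beta CDF(0.2; 1+y, 1+n−y) is below 0.1. This probability equals P(Bin(n+1, 0.2) ≥ y+1), which gives a cross-check. All 45 printed values match (for example k=4 at N=10, 8 at N=25, 14 at N=51, 15 at N=54). The arithmetic is sound; the question is only what goes into y.

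**Step 2: direction of the effect.** With 3 events in 9 subjects, P(θ<0.2) = Beta CDF(0.2; 4, 7) = 0.121. Suppose the tenth subject's pneumonitis is recorded only as grade 5.

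- As written, y=3 and n=10: Beta CDF(0.2; 4, 8) = 0.161. The arm looks safer than before the death.
- If counted, y=4 and n=10: Beta CDF(0.2; 5, 7) = 0.050. The arm stops.

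**Step 3: one uncounted case at the boundary.**

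| N | Grade 3/4 + grade 5 only | P(θ<0.2) as written | P(θ<0.2) if counted |
|---|---|---|---|
| 10 | 3 + 1 | 0.161, continue | 0.050, stop |
| 25 | 7 + 1 | 0.131, continue | 0.059, stop |
| 51 (Arm 2 maximum) | 13 + 1 | 0.142, continue | 0.082, stop |
| 54 (Arm 1 maximum) | 14 + 1 | 0.121, continue | 0.069, stop |

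**Step 4: effect on the chance of stopping.** This needs assumptions, because the documents give no fatal share. Take a true rate of grade 3 or higher of 25%, and let f be the share of those cases that are fatal. The probability of crossing the printed boundary is computed by exact recursion, with a look after every subject from N=10 to the arm's maximum. The per-subject probability of a counted event is:

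- 0.25 if fatal cases count;
- 0.25 × (1−f) if no fatal case was first counted as grade 3/4 (upper bound on the loss);
- 0.25 × (1−f/2) if half were already counted.

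| Probability of stopping | f=5% | f=10% | f=20% | f=30% |
|---|---|---|---|---|
| Arm 1, fatal cases count | 65% | 65% | 65% | 65% |
| Arm 1, half already counted | 62% | 58% | 51% | 44% |
| Arm 1, none already counted | 58% | 51% | 37% | 24% |
| Arm 2, fatal cases count | 64% | 64% | 64% | 64% |
| Arm 2, half already counted | 61% | 57% | 50% | 43% |
| Arm 2, none already counted | 57% | 50% | 36% | 24% |

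If all fatal cases were already counted, nothing is lost.

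**Step 5: add the death rule.** Step 4 models the pneumonitis boundary alone. Adding automatic termination at two or more deaths in 10, or three or more in 25, and taking every fatal case as definitely related and none as previously counted, Arm 1 stops automatically with probability 59/53/48/51% at f = 5/10/20/30%. If half the fatal cases are judged definitely related, the figures are 58/52/40/32%. The comparator with fatal cases counted also rises: at f=30% with all definitely related it is about 70%, against 51%. The death rule narrows the gap at high fatal shares and does not close it.

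**The case against.** The strongest reply is that section 13.8 is silent on grade 5 rather than excluding it, and that the split may be deliberate. Non-fatal cases go to the pneumonitis rule; deaths go to a rule with much lower thresholds (2 of 10 and 3 of 25, against 4 of 10 and 8 of 25). In the N=10 example, a definitely related death would by itself require DSMB discussion. Monitoring is continuous, so most severe cases may be recorded at grade 3 or 4 before death. Beyond DSMB review and SAE reporting, the sponsor-investigator assesses the relatedness of every SAE (section 12.2.2.3) and investigators review safety continuously (section 14.1). Finally, adding grade 5 under the same 20% limit changes the monitored quantity and makes stopping more likely.

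Part of this stands. Continuing at N=10 describes the pneumonitis rule, not the whole plan. The low figures at 20% and 30% fatal need several assumptions together, including that no fatal case is judged definitely related. The backstops are real.

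The rest does not remove the problem. Definite is one of five relatedness categories in section 12.1.4, and section 11.1.8 says that drug-related and unrelated pulmonary findings can be hard to tell apart in NSCLC. A fatal case judged possibly or probably related, and recorded only as grade 5, meets neither numeric rule. A single definitely related death at the 25-subject look has no stated action, and no numeric death rule is stated after that look. If the intention was always to count grade 5, writing it down costs nothing.

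**Conclusion.** The concern holds. Taken literally, the rule gives a wrong-direction result for a pneumonitis case recorded only as grade 5, and one such case can turn a stop into a continue at N=10, 25, 51 and 54. That conclusion follows from the event definition and the Beta model and needs no assumed fatal share.

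The overall loss of stopping probability does depend on assumptions: a 25% true rate, the fatal share, how many fatal cases were already counted at grade 3 or 4, and how many deaths are judged definitely related. It runs from nothing, if all were already counted, to an upper bound for the pneumonitis rule in Arm 1 of 65% falling to 58% at a 5% fatal share and to 24% at 30%. The gap is in the numeric trigger, not in oversight as a whole. It should be fixed.

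**What to change.** In section 13.8, define y as pneumonitis of grade 3 or higher, including grade 5, and state that a case stays counted if it becomes fatal. Use the same wording in the sentence on continuous monitoring and in the criterion. The prior, the 20% limit, the 0.1 cut-off and the k table stay as they are. The attribution level of the death rule, and its coverage after subject 25, are for the sponsor and DSMB and are not part of this change.

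The cost is one sentence, with no new data and no new table. The downside is a higher chance of stopping an arm in which fatal pneumonitis occurs although the true rate is below the limit. With 20% of cases fatal (assumed) and none previously counted, the counted rate moves from 0.10 × 0.8 = 0.08 to 0.10, and Arm 1 stopping by N=54 rises from 1.4% to 3.3%. At a true rate of 15% (0.12 to 0.15) it rises from 6.4% to 14.3%. With no fatal cases nothing changes.

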## Thresholds "k" for N=10 to N=54

## 14. TRIAL MANAGEMENT

## 14.1 Data and Safety Monitoring Plan (DSMP)

The study will be conducted in accordance with the Indiana University Melvin and Bren Simon Cancer Center's (IUSCC) DSMP for moderate risk trials.

BTCRC AHQ facilitated oversight activities include:

- Review and process all adverse events requiring expedited reporting as defined in the protocol
- Notify participating sites of adverse events requiring expedited reporting
- Provide trial accrual progress, safety information, and data summary reports to the sponsorinvestigator
- Investigators will conduct continuous review of data and patient safety

## 14.2 Data Safety Monitoring Board

This study will have a Data and Safety Monitoring Board (DSMB). The DSMB is chaired by an independent medical oncologist external to this trial. The DSMB will provide a recommendation to the sponsor-investigator after all information is reviewed. This information will also be provided to BTCRC AHQ who will distribute to the site investigator/participating sites for submission to their respective IRB according to the local IRB's policies and procedures.

The DSMB will meet after the first 10 subjects are treated with at least one dose of study drug and observed for a minimum of 3 months after first dose of study therapy, in each arm respectively. Accrual will not be held while the DSMB review is pending. Each arm will be scrutinized separately and may result in different actions per arm.

The DSMB will also meet after the first 25 subjects are treated with at least one dose of study drug and observed for a minimum of 3 months after first dose of study therapy, in each arm respectively. Accrual will not be held while the DSMB review is pending. Each arm will be scrutinized separately and may result in different actions per arm.

From the time of first subject enrollment until the last subect completes study drug administration, the DSMB will conduct reviews at least twice a year.

The DSMB review will include but is not limited to:

- Study accrual patterns
- Treatment regimen information
- Adverse event summary report
- Summary of any deaths on study including cause of death
- Audit and/or monitoring results, if applicable
- Protocol deviations

#### 14.3 Data Quality Oversight Activities

Remote validation of Oncore data will be completed on a continual basis throughout the life cycle of the study. A summary report (QC Report) of these checks together with any queries resulting from manual review of the eCRFs will be generated for each site and transmitted to the site and the site monitor. Corrections will be made by the study site personnel.

Monitoring visits to the trial sites will be made periodically during the trial to ensure key aspects of the protocol are followed. Additional for-cause visits may occur as necessary. Source documents will be reviewed for verification of agreement with data entered into OnCore. It is important for the site investigator and their relevant personnel to be available for a sufficient amount of time during the monitoring visits or audit, if applicable. The site investigator and institution guarantee access to source documents by BTCRC AHQ or its designee.

The trial site may also be subject to quality assurance audit by BMS or its designee as well as inspection by appropriate regulatory agencies.

## 14.4 Compliance with Trial Registration and Results Posting Requirements

Under the terms of the Food and Drug Administration Modernization Act (FDAMA) and the Food and Drug Administration Amendments Act (FDAAA), the sponsor-investigator of the trial is solely responsible for determining whether the trial and its results are subject to the requirements for submission to the Clinical Trials Data Bank, http://www.clinicaltrials.gov. All results of primary and secondary objectives must be posted to CT.gov within a year of completion. The sponsor-investigator has delegated responsibility to BTCRC AHQ for registering the trial and posting the results on clinicaltrials.gov. Information posted will allow subjects to identify potentially appropriate trials for their disease conditions and pursue participation by calling a central contact number for further information on appropriate trial locations and study site contact information.

## **15. DATA HANDLING AND RECORD KEEPING**

#### 15.1 Data Management

BTCRC AHQ will serve as the Clinical Research Organization for this trial. Data will be collected through the web-based clinical research platform, OnCore, a system compliant with Good Clinical Practices and Federal Rules and Regulations. BTCRC AHQ personnel will coordinate and manage data for quality control assurance and integrity. All data will be collected and entered into OnCore by study site personnel from participating institutions.

#### **15.2** Case Report Forms and Submission

Generally, clinical data will be electronically captured in OnCore and correlative results will be captured in OnCore or other secure database(s). If procedures on the study calendar are performed for standard of care, at minimum, that data will be captured in the source document. Select standard of care data will also be captured in OnCore, according to study-specific objectives. Please see the Data and Safety Oversight Process (DSOP) guidelines for further details.

The completed dataset is housed at BTCRC AHQ and is the sole property of the sponsor-investigator's institution. It should not be made available in any form to third parties, except for authorized representatives of appropriate Health/Regulatory Authorities, without written permission from the sponsor-investigator and BTCRC AHQ. After the initial publication, the complete data set will be available to all BTCRC institutions.

## **15.3** Record Retention

To enable evaluations and/or audits from Health Authorities/BTCRC AHQ, the site investigator agrees to keep records, including the identity of all subjects (sufficient information to link records; e.g., hospital records), all original signed informed consent forms, copies of all source documents, and detailed records of drug disposition. All source documents are to remain in the subject's file and retained by the site investigator in compliance with local and federal regulations. No records will be destroyed until BTCRC AHQ confirms destruction is permitted.

## 15.4 Confidentiality

There is a slight risk of loss of confidentiality of subject information. All records identifying the subjects will be kept confidential and, to the extent permitted by the applicable laws and/or regulations, will not be made publicly available. Information collected will be maintained on secure, password protected electronic systems. Paper files that contain personal information will be kept in locked and secure locations only accessible to the study site personnel.

Subjects will be informed in writing that some organizations including the sponsor-investigator and his/her research associates, BTCRC AHQ, BMS, IRB, or government agencies, like the FDA, may inspect their medical records to verify the information collected, and that all personal information made available for inspection will be handled in strictest confidence and in accordance with local data protection laws.

If the results of the study are published, the subjects' identities will remain confidential.

## 16. ETHICS

## 16.1 Institutional Review Board (IRB) Approval

The final study protocol and the final version of the informed consent form must be approved in writing by an IRB. The site investigator must submit written approval by the IRB to BTCRC AHQ before he or she can enroll subjects into the study.

The site investigator is responsible for informing the IRB of any amendment to the protocol in accordance with local requirements. In addition, the IRB must approve all advertising used to recruit subjects for the study. The protocol must be re-approved by the IRB as local regulations require.

Progress reports and notifications of adverse events will be provided to the IRB per local regulations and guidelines.

## 16.2 Ethical Conduct of the Study

The study will be performed in accordance with ethical principles originating from the Declaration of Helsinki. Conduct of the study will follow ICH Good Clinical Practice, and with all applicable federal (including 21 CFR parts 56 & 50), state, or local laws.

#### 16.3 Informed Consent Process

The site investigator will ensure the subject is given full and adequate oral and written information about the nature, purpose, possible risks and benefits of the study. Subjects must also be notified they are free

to discontinue from the study at any time. The subject should be given the opportunity to ask questions and allowed time to consider the information provided.

The subject's signed and dated informed consent must be obtained before conducting any procedure specifically for the study. The site investigator must store the original, signed informed consent form. A copy of the signed informed consent form must be given to the subject.

## **18. APPENDIX 1: ADVERSE EVENT MANAGEMENT ALGORITHMS**

These general guidelines constitute guidance to the site Investigator and may be supplemented through discussions with the Sponsor-Investigator by contacting the BTCRC project manager. The guidance applies to all immuno-oncology agents and regimens.

As general principle, differential diagnoses should be diligently evaluated according to standard medical practice. Non-inflammatory etiologies should be considered and appropriately treated.

[figure not shown]
Corticosteroids are a primary therapy for immuno-oncology drug-related adverse events. The oral equivalent of the recommended IV doses may be considered for ambulatory patients with low-grade toxicity. The lower bioavailability of oral corticosteroids should be taken into account when switching to the equivalent dose of oral corticosteroids.

Consultation with a medical or surgical specialist, especially prior to an invasive diagnostic or therapeutic procedure, is recommended.

The frequency and severity of the related adverse events covered by these algorithms will depend on the immuno-oncology agent or regimen being used.

